## PROTOCOL TITLE: Restore: Gay Men and Prostate Cancer Aim III

To ensure our structured rehabilitation program is evidence-based and state-of-the-art best practice, we conducted a systematic literature search using “prostate” and synonyms by “sexual rehabil\*” “urine”, and synonyms, since 1980, in English, French or Spanish. This yielded 614 references. We highlight three findings. First, of the 614 papers, only 127 (20.7%) focused on rehabilitation. Rehabilitation appears an under-researched area relative to treatment. Second, with few exceptions, research on rehabilitation has focused on UI or ED as separate issues and taken a component approach to studying treatment. But UI and ED often occur together; and are the top two challenges patients ask for help with, online. Combination treatment permits study of both outcomes. We conclude a structured treatment program tailored for GBM is the appropriate first (and next) step in advancing treatment for GBM with PCa.

Many PCa rehabilitation studies equate erectile functioning with vaginal sex; few studies have examined other sexual problems. For example, only two papers have examined climacturia. The first estimated 20% of otherwise continent men experience it after radical prostatectomy, and showed it increased survivors’ sexual anxiety, avoidance of sex, and low orgasmic satisfaction. The second estimated prevalence, 4-years post-treatment, to be 33.9%. No treatment studies have been published or used climacturia as a primary end point, a gap this study will address.

Of the 614 articles reviewed, 612 focused on vaginal intercourse or erections. None were in GBM. There have been no studies (in heterosexuals or GBM) of rehabilitation for insertive anal sex, receptive anal sex, and no studies to treat climacturia. This absence makes it literally impossible for clinicians to practice evidence based medicine with GBM patients. The IOM concludes this failure of science creates and sustains GBM health disparities.

As reflected in the small size of the few published studies, recruitment has been a major barrier impeding GBM with PCa research. Given our success in recruiting the largest sample to date, we are the right team to test new methods for recruitment.

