### 6.2 Study Procedures:

Following successful screening (see below), participants will review an online consent form which overview the study, study tasks, outlines risks and benefits, strategies to reduce risks, and risk-benefit analysis. After this, they participate in an initial telephone call from the project coordinator where they have the opportunity to ask any questions and have them answered, as well as verify information for cross-validation purposes. Then, if confirmed eligible and unique, they receive access to the baseline survey. Participants who complete the baseline survey will then be randomized, via a computer assignment, to a treatment or control group.

Participants in the control group will be notified by email. Thereafter, they will be contacted occasionally with survey links and reminders. As needed, additional casual communications will be used to increase retention.

Participants in the treatment group will be emailed immediately with a username and password to access the intervention. They will be mailed their welcome packet within one week.

Surveys will be conducted at baseline, and at 3, 6, 9, 12, 18, and 24 months follow-up. Surveys are attached.

Interaction for all participants in our study will include an online screening survey, a vetting phone conversation, an email confirmation, followed by an online baseline survey and five follow-up surveys. In addition, all participants can contact the study at any time using a 1-800 and/or our study email. In all email and phone contact, we will maintain HIPPA compliant standards to ensure no privacy violations. (e.g., we will not describe the nature of the study in phone or email messages). In addition, data will be maintained in password protected files on a secure server.

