**10.0 Study Population**

**10.1 Inclusion Criteria:**

Each participant must be:

- An adult biological male who has had sex with a man or men
- Diagnosed with PCa and treated or pending treatment, including but not limited to radical prostatectomy, radiation, and/or hormone therapy
- Recent problems with sexual and/or urinary function
- Living in the United States or its territories
- A unique, validated individual

PROTOCOL TITLE: Restore: Gay Men and Prostate Cancer Aim III

10.2 Exclusion Criteria:

- Cognitive Impairment
- Non-English speaking/reading
- Patients who underwent a bi-lateral, non nerve-sparing, prostatectomy (for which rehabilitation is not recommended as efficacious).

10.3 Screening:

Participants will complete an online screening survey to evaluate inclusion criteria (attached). Upon completion of the screener, study staff will call each participant to confirm identity, confirm screening survey answers and evaluate English and cognitive proficiency. Participants' IP addresses will be used to ensure US location and deduplication.

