ID: SPH-2018-26507

NCT03343093

November 13, 2023

Title: Restore: Improving Sexual Outcomes of Gay and Bisexual Prostate Cancer Survivors

Statistical Analysis Plan

Data Analysis Plan (NCT03343093)

The purpose of Hypothesis 3.1 is to test whether structured rehabilitation (intervention) will yield statistically significantly better QoL, sexual and urinary outcomes than routine care (control) over 24 months. The data to be analyzed will comprise of 9 measurement occasions (1 baseline measurement, 7 quarterly measurements and 1 final measurement). The primary outcomes are: (1) sexual function measured by overall SF and EPIC sexual function and bother scores, and (2) urinary function measured by overall UI and EPIC urinary function and bother scores. We will use a mixed-effects model for repeated measures data to investigate the difference in the overall improvement trajectory between the intervention group vs. the control group over 24 months of the study on the primary outcome variables. If we find the statistical evidence to support our hypothesis, we will run an additional secondary analysis where we will compare different facets/components of the intervention. That is, we will investigate the main effects, along with the interaction effects among the different components of the intervention. To test for Hypothesis 3.2, we will incorporate treatment type, demographics, and health status as moderator variables into the statistical framework of mixed-effects models. We will evaluate Hypothesis 3.3 to test whether the effects of intervention are greater in newly treated men (<2 years since prostate cancer treatment) vs. men 2+ years, post-treatment. We will analyze this hypothesis by using the grouping variable (early vs. long term) in the mixed-effects model to study the difference in the improvement trajectory of the two levels of this grouping variable. To evaluate Hypothesis 3.4 we will assess if the overall slope coefficient for the men 2+ years post-treatment obtained from the mixed-effects model is statistically significant. The analysis of Hypothesis 3.5 would include the dependent variable of Climacturia, measured by single items from the GSFS scale, and the intervention components of pelvic floor exercises and PDE5-I drugs are the predictors/independent variables. We will test if pelvic floor exercises and PDE5-I drugs can predict improvement in Climacturia over time by using a mixed-effects model.

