Power Estimation. We expect 80% power to detect the statistically significantly differences between the intervention group and the control group. The power calculation was based on standardized effect size = 0.35, total number of observations per participant during the course of the study, $M = 9$, total number of participants, $N = 450$, assumed within-subject variability, $\sigma^2 = 0.50$, assumed between-subject variability, $\tau^2 = 0.20$ and a linear change over time.

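### SAP Hypothesis 3.5 tests improvement in climacturia without a baseline-climacturia condition or adjustment, so the estimate may be diluted and self-chosen component use may predict improvement without causing it

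*SAP*

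**What the plan says.** Climacturia is the secondary outcome in protocol section 4.2. The SAP's Data Analysis Plan takes it up as Hypothesis 3.5. The dependent variable is single items of the gay sexual functioning scale, and the predictors are two intervention components: "We will test if pelvic floor exercises and PDE5-I drugs can predict improvement in Climacturia over time by using a mixed-effects model". The text gives no analysis set, no condition on baseline climacturia and no baseline covariate. The optional adjusters in protocol section 17.3 (treatment time, relationship status, comorbidities, demographics) do not include baseline climacturia.

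The relevant entry criterion in section 10.1 is "Recent problems with sexual and/or urinary function". Climacturia is not required, and men whose treatment is still pending may enter.

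Section 2.0 of the protocol cites two rates: "The first estimated 20% of otherwise continent men experience it after radical prostatectomy", and "The second estimated prevalence, 4-years post-treatment, to be 33.9" per cent.

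Under section 5.1, sildenafil is optional, and the pelvic floor exercises are meant to help both urinary incontinence and climacturia. The trial randomises men to the whole programme or to usual care, not to components.

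The only power statement is for the comparison of arms: "We expect 80% power to detect the statistically significantly differences between the intervention group and the control group". None is given for Hypothesis 3.5.

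**The concern.** Improvement can occur only in a man who has the symptom. A man without climacturia at baseline can stay as he is or get worse. A single model over a mixed group therefore has two problems.

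- **Dilution.** The average change is the change in affected men multiplied by their share, with new onset in the others set against it. A small estimate could mean a weak effect in affected men, or a good effect in a few of them.
- **Confounding by baseline status.** Component use is the man's own choice. If men with climacturia do the exercises more often, and some of them recover anyway, then use marks the men with room to improve. It would predict improvement even if the exercises did nothing.

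Section 2.0 presents the lack of climacturia treatment studies as a gap that this trial will help to fill, so the result is likely to be read as evidence on treatment.

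**Working it through.** **1. The plan's own power figure.** Inputs from the SAP's Power Estimation paragraph: N = 450, effect size 0.35, M = 9, within-subject variance 0.50, between-subject variance 0.20, linear change. Assumed, because not stated: two-sided 5% test, time in years with quarterly occasions, effect in units of the between-subject SD of slopes.
- Slope sampling variance: V = 0.50 / Σ(t − mean t)² = 0.50 / 3.75 = 0.133.
- Reliability: 0.20 / (0.20 + 0.133) = 0.60.
- Noncentrality: 450 × 0.35² × 0.60 / 4 = 8.27.
- Power from noncentral F(1, 448): 81.8%, close to the stated 80%.

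With the seven surveys of protocol section 6.2 in place of nine occasions, power is 78.0%. Both figures concern intervention against control, not Hypothesis 3.5.

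**2. Men with room to improve.** Let p be the share with climacturia at baseline. The value 50% is my assumption, because the trial enrols men who already have problems.

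| p | affected men of 450 | without the symptom | a 0.5 SD benefit in affected men, averaged over all |
|---|---|---|---|
| 20% | 90 | 80% | 0.5 × 0.20 = 0.10 SD |
| 33.9% | 153 | 66.1% | 0.5 × 0.339 = 0.17 SD |
| 50% | 225 | 50% | 0.5 × 0.50 = 0.25 SD |

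The shrinkage factor is p itself and does not depend on noise. New onset would change the average further.

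**3. Power, as a by-arm illustration.** Hypothesis 3.5 specifies no by-arm test; this only shows the scale. Take d = 0.5 in affected men (assumed), and let k be the noise SD of unaffected men relative to affected men. The variance over all men is p + (1 − p)k² + p(1 − p)d²/4, and the all-men effect is 0.5p divided by its square root. For p = 0.20 and k = 1 the variance is 0.20 + 0.80 + 0.01 = 1.01, the effect is 0.10/√1.01 = 0.0995, and power with 450 men is 18%.

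| p | all men, k = 1 | all men, k = 0.5 | all men, k = 0 | affected men only |
|---|---|---|---|---|
| 20% | 18% | 38% | 64% | 65% (n = 90) |
| 33.9% | 43% | 70% | 86% | 87% (n = 153) |
| 50% | 75% | 91% | 96% | 96% (n = 225) |

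Men at the floor of an item should vary less than affected men, so k = 1 is the extreme case. A simulation with a floored 0-4 item and 450 men gave a smaller gain from restriction: 43% to 54% at p = 20%, and 69% to 76% at p = 33.9%.

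**4. False prediction with no component effect.** Take 225 intervention men, with exercise use by 70% of affected and 40% of unaffected men (assumed).
- At p = 20%, the share affected is 0.14/(0.14 + 0.32) = 30.4% among users and 0.06/(0.06 + 0.48) = 11.1% among non-users. With 0.5 SD natural recovery in affected men (assumed), users appear better by 0.5 × (0.304 − 0.111) = 0.10 SD.
- At p = 33.9%, the shares are 0.237/(0.237 + 0.264) = 47.3% and 0.102/(0.102 + 0.397) = 20.4%, and the apparent benefit is 0.13 SD.

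Simulated false-positive rates at a nominal 5% (p = 20% and 33.9%, k = 1 and 0.5):

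| natural recovery in affected men | all men, unadjusted |
|---|---|
| 0.5 SD | about 10-26% |
| 0.25 SD | about 7-12% |
| none | about 5% |

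Restricting to affected men, or adjusting for baseline climacturia yes/no, brings the rate back to about 5%.

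**5. What restriction leaves.** Suppose half of the affected men are severe, use the exercises more (85% against 55%) and recover more (0.75 against 0.25 SD), all assumed. The restricted test still gives about 8-10% false positives. Adjusting for severity removes this in the same model.

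**The case against.** - **The SAP does not say that all men are analysed.** That is an inference from silence, and component use may be modelled in the intervention arm only. This stands. But nothing in the text excludes men without the symptom, and the intervention arm has the same mix.
- **A reader might infer that the protocol's own rates show 66% to 80% of this sample to be free of climacturia.** They do not. The 20% is for otherwise continent men after prostatectomy; the 33.9% is from another sample four years after treatment. Selecting men with problems may raise the rate here, and other or pending treatments may lower it. The range is an assumption.
- **A reader might infer that restriction would restore power.** Much of the low power comes from the small number of affected men, which no choice of analysis set can cure. If unaffected men add no noise, restriction gains almost nothing in power and only the estimate is clearer.
- **A reader might infer that a false finding is to be expected.** The documents give neither uptake by symptom nor a recovery rate. The exercises are offered to every intervention man and serve incontinence too. Without natural recovery the test keeps its level.
- **An all-men mean is not meaningless.** It describes net burden, including prevention. That is a fair supportive result, but not improvement in men with the symptom.
- **Baseline adjustment would control the false positives and keep every man.** This is true for baseline yes/no, and it is why an adjusted all-men model belongs in the fix. It does not by itself give the effect in affected men.
- **The item's scale cannot be seen,** because the surveys are attachments. The size of the floor is therefore unknown.

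**Conclusion.** The concern holds in a limited form. Hypothesis 3.5 is about improvement, but the SAP neither limits it to men who can improve nor adjusts for baseline climacturia, and eligibility does not do so either. If 20% to 50% of the sample is affected, half or more of the men cannot improve, and the average improvement is 0.2 to 0.5 of that in affected men. This part needs only the prevalence assumption.

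The power loss ranges from large to negligible with the noise in unaffected men, and it is shown for a by-arm test that Hypothesis 3.5 does not specify. False prediction needs both symptom-driven use and untreated recovery; it is plausible because use is chosen, but the documents do not establish it. The stated 80% power is not contradicted, since it covers a different comparison. This is a gap in a secondary hypothesis that should be closed. It does not affect the primary analysis.

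**What to change.** In the SAP text for Hypothesis 3.5:

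1. Run the improvement model in men who report climacturia on the baseline survey, with baseline severity as a covariate. Protocol section 6.2 places that survey before randomisation, so a comparison of arms within this set stays valid.
2. In men without climacturia at baseline, report new onset as a separate result.
3. Give the all-men model as supportive, with baseline climacturia and its interaction with time.
4. State whether the component model uses both arms or the intervention arm only, and label its results as non-randomised associations.

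The cost is SAP wording, provided that the climacturia items are on the baseline survey, which should be confirmed. The main climacturia estimate will rest on fewer men (90 to 225 of 450 on the assumed range, or half that in the intervention arm alone). Any preventive effect is then read from the new-onset result. Confounding by unmeasured factors remains.
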